14.4.2. Clinical Laboratory Tests

Laboratory data will be summarized by type of laboratory test. Descriptive statistics will be calculated for each laboratory analyte at baseline and for observed values and changes from baseline at each scheduled time point. Changes from baseline results will be presented in pre- versus posttreatment cross-tabulations (with classes for below, within, and above normal ranges). A listing of patients with any laboratory results outside the reference ranges will be provided.

Laboratory parameters with predefined NCI-CTCAE toxicity grades will be summarized. Change from baseline to the worst adverse event grade experienced by the patient during the study will be provided as shift tables.

14.4.3. Electrocardiogram

Summary statistics will be provided for the ECG intervals and their changes from baseline by dose group and cohort.

Exposure-QTcF analysis of TRC253 will be performed using triplicate \pm 5 minute time points ECG measurements. TRC253 plasma concentrations from Cycle 1 Day 1 and Cycle 3 Day 1 and at steady state timepoints will be used for the exposure-QTcF analysis.

14.4.4. Vital Signs

The incidence of abnormalities in vital signs including temperature, heart rate, and blood pressure will be assessed.

14.4.5. Physical Examination

Abnormal physical examination findings at screening and during the study will be provided in a listing.

14.5. Pharmacokinetic Analyses

All plasma concentrations below the lowest quantifiable concentration or missing data will be labeled as such in the concentration data presentations or SAS dataset. Concentrations below the lower quantifiable concentration will be treated as zero in the summary statistics. All patients and samples excluded from the analysis will be clearly documented in the Clinical Study Report.

Data will be listed for all patients with available plasma concentrations per dose level/Part. Patients will be excluded from the PK analysis if their data do not allow for accurate assessment of the PK (e.g., incomplete administration of the study drug; missing information of dosing and sampling times; concentration data not sufficient for PK parameter calculation).

Descriptive statistics will be used to summarize TRC253 plasma concentrations at each sampling time point, by dose level/study part. Pharmacokinetic parameters of TRC253 will be determined using non-compartmental analysis and summarized by dose level/study part. Mean and individual plasma TRC253 concentration time profiles will be plotted (linear and semilog) after the first dose of study drug and at steady state. Analysis of dose proportionality and steady state versus Day 1 accumulation ratios will be conducted.

A snapshot date for PK samples to be analyzed may be defined, if required. Samples collected before this date will be analyzed for TRC253 and included in the PK analysis. Samples collected after the snapshot date may be analyzed at a later date, and may be included in a PK re-analysis when they become available after database lock.

Population PK analysis of plasma concentration-time data of TRC253 will be performed using nonlinear mixed-effects modeling. Available baseline patient characteristics (demographics, laboratory variables, race, etc.) will be tested as potential covariates affecting PK parameters. Data from this study may be pooled with other data for the population analysis. Details will be given in a population PK analysis plan and the results of the population PK analysis will be presented in a separate report.

14.6. Biomarker Analyses

14.6.1. FDHT-PET

The maximum standard uptake value will be calculated for each lesion at each tested dose level and for all lesions. The percent decline in maximum standard uptake will be directly proportional to AR occupancy and therefore can be used to estimate EC₉₀ which will be taken into consideration to select the RP2D.

14.6.2. Exploratory Biomarkers

CTC number at baseline, and change in CTC counts will be descriptively summarized. Prostate-specific antigen changes at Week 12 will be correlated with expression of molecular markers to identify novel sensitizing mechanisms. Whole blood and plasma samples collected will be used to estimate frequency of expression of resistance and high risk markers. Associations will be made with time to clinical endpoints and expression of resistance biomarkers.

The association of biomarkers with clinical response or relevant survival endpoints may be assessed using appropriate statistical methods (e.g., analysis of variance, categorical or survival models) depending on the endpoints. Analyses may be performed within the treatment group. Other clinical covariates (such as baseline tumor characteristics and patient demographics) may also be included in the model. Correlation of baseline biomarker expression levels with clinical response or relevant time to-event endpoints may be performed to identify responsive (or resistant) subgroups. Association of biomarkers with clinical response or relevant time-to-event endpoints will also be explored in the overall population. Appropriate details of these exploratory analyses will be included in the statistical analysis plan. Results of these exploratory analyses will be presented in separate technical reports.

14.7. Pharmacokinetic/Pharmacodynamic Analyses

Pharmacokinetic/pharmacodynamic (PK/PD) analyses will be performed using data from all patients who have sufficient data available to evaluate anti-tumor effects of TRC253. The population PK/PD analysis will use concentration as an independent variable. Pharmacodynamic endpoints such as percent decline in average maximum standardized uptake value ($SUV_{max-avg}$) from baseline (estimate EC_{90}) from FDHT-PET, time to PSA progression, and percent change in PSA relative to baseline will be considered using non-linear mixed-effect modeling analysis.

14.8. Efficacy Analyses

Patient listings will be provided for efficacy evaluations including PSA response rate, time to PSA progression, and rPFS.

Post-treatment percent change in PSA relative to baseline will be reported at Week 12 (or earlier for those who discontinue therapy), and separately, the maximal change at any time on study will also be reported for each patient and summarized using waterfall plots.

For Part 2, efficacy summaries by population cohort will be performed. Median time to PSA progression will be determined separately for each of the expansion cohorts and Kaplan-Meier curves may be plotted. If there is sufficient data, rPFS will be summarized and median rPFS will be assessed. If deemed appropriate, patients receiving the same dose from Part 1 may also be combined with Part 2 patients.

15. DIRECT ACCESS TO SOURCE DATA/DOCUMENTS

All data entered on CRFs/eCRFs must be verifiable within the patients' source documents (written or electronic record). The Investigator/institution guarantees TRACON representatives and appropriate regulatory authorities direct access to the original source records for the duration of the agreed study record retention period. Printouts of source records that are electronically obtained and stored will not be acceptable for audit/inspection unless provided as certified exact copies and the data remains as meaningful and useful as in its original electronic state. All eCRF entries, corrections, and alterations must be made by the investigator or authorized study-site personnel. The investigator must verify that all data entries in the eCRF are accurate and correct.

Legally protected patient identification and other personal health information must be securely stored with limited access by the participating institutions. Unless secure provisions are established by the institution to allow TRACON (or designee) to perform remote monitoring of electronic source records, TRACON (or designee) will review source records/data on site and will not remove any such protected health information.

In addition to on-site monitoring visits, remote contacts can occur. It is expected that during these remote contacts, study-site personnel will be available to provide an update on the progress of the study at the site.

16. QUALITY CONTROL AND QUALITY ASSURANCE

Monitoring visits to clinical investigator sites will be made by TRACON or its representatives periodically during the trial to ensure that GCPs and all aspects of the protocol are being followed.

Representatives of the sponsor's clinical quality assurance department may visit the study site at any time during or after completion of the study to conduct an audit of the study in compliance with regulatory guidelines and company policy. The trial site will also be subject to possible inspection by the institutional review board (IRB) or independent ethics committee (IEC) or other appropriate regulatory authority. The investigator should immediately notify the sponsor if he or she has been contacted by a regulatory agency concerning an upcoming inspection.

It is important that the Investigator(s) and their relevant personnel are available during the monitoring visits, audits, and inspections and that sufficient attention, time, and support is devoted to the process.

TRACON and its representatives will be governed by applicable regulations, good clinical practice standards, and internal SOPs for the conduct of monitoring visits and QA audits. Protocol deviations will be captured in TRACON's electronic data capture system.

17. ETHICS

17.1. Health Authorities and Independent Ethics Committees/Institutional Review Boards

This study will be undertaken only after the IEC/IRB has given full approval of the final protocol, amendments (if any, excluding the ones that are purely administrative, with no consequences for patients, data or study conduct, unless required locally), the ICF, applicable recruiting materials, and patient compensation programs, and the sponsor has received a copy of this approval. This approval letter must be dated and must clearly identify the IEC/IRB and the documents being approved.

All correspondence and other evidence of appropriate and timely communications with the IRB/IEC should be retained in the Investigator/site files. Copies of all IRB/IEC approvals should also be forwarded to TRACON.

The only circumstance in which an amendment may be initiated prior to relevant approval is where the change is necessary to eliminate apparent immediate hazards to the patients. In that event, the Investigator must notify the IRB/IEC/health authorities and TRACON in writing within 5 business days after the implementation.

At the end of the study, the investigator (or sponsor where required) will notify the IEC/IRB about the study completion.

17.2. Ethical Conduct of the Study

The investigator is responsible for ensuring the trial is performed in accordance with the protocol, applicable local regulatory requirements and laws, and the International Conference on Harmonization Guideline on Good Clinical Practice, which supports the application of ethical principles that have their origin in the Declaration of Helsinki (see ICH E6, §2.1).

17.3. Written Informed Consent

The informed consent form language must be agreed upon by TRACON and the IRB/IEC and must be in compliance with ICH GCP, local regulatory requirements, and legal requirements. The informed consent information must not be changed without prior approval by TRACON and the IRB/IEC. The informed consent form used in this trial, and any changes made during the course of the trial, must be approved by both the IRB/IEC and TRACON, or designee, before use.

It is the responsibility of the Investigator to give each patient full and adequate verbal and written information regarding the objective and procedures of the trial and the possible risks involved. This information must be provided to each patient prior to undertaking any trial-related procedure. The patient will be given sufficient time to read the ICF and the opportunity to ask questions. After this explanation and before entry into the study, consent should be appropriately recorded by means of the patient's personally dated signature. After having obtained the consent, a copy of the ICF must be given to the patient.

Each patient must be informed about her right to withdraw from the trial at any time. Furthermore, it is the responsibility of the Investigator to ensure each patient is appropriately

informed before obtaining signed and dated consent. Signatures from the investigator conducting the informed consent discussion should also be obtained prior to undertaking any trial-related procedure. Consent by a legally authorized representative is not permitted. Should an impartial witness be needed, ICH E6 requirements for impartial witnesses will apply.

The Investigator will retain each patient's original signed consent form in the Investigator/site files.

17.4. Patient Compensation

Patients will not be compensated for participation in this trial; this will be outlined in the informed consent form.

18. DATA HANDLING AND RECORDKEEPING

18.1. Inspection of Records

CRFs are required and should be completed for each patient who receives treatment with TRC253. Screen failure CRFs will not be collected. Nevertheless, records of potential patients identified and screened shall be retained on site screening logs. The completed original CRFs are the sole property of TRACON and should not be made available in any form to third parties without written permission from TRACON (except for authorized representatives of the HRA and in accordance with HIPAA regulations).

It is the Investigator's responsibility to ensure completion and to review and approve all CRF data. The investigator will sign off on his/her data per patient. These signatures serve to attest that the investigator has reviewed and approved the information contained on the case report forms and that the information is complete, accurate, and true. At all times, the Investigator has final personal responsibility for the accuracy and authenticity of all clinical and laboratory data entered on the CRFs.

The use of electronic CRFs (eCRFs) to capture study data using automated computerized data capture systems does not change the principles and requirements for collecting study data. The investigator still retains final personal responsibility for eCRF data and any associated data pertaining to it (e.g. metadata including any record of change to the originally recorded data). The investigator's signed approval of the eCRF data serves to attest that the electronic data and all of its associated metadata (including changes) has been reviewed and accepted as complete, accurate, and true for each patient in the study.

All CRF/eCRF data must be verifiable in the patient's source records by TRACON or its designee. TRACON will review CRF data as compared to source records in an attempt to identify missing and spurious data and notify the investigator of findings so that proper corrections can be made. TRACON representatives (monitors and auditors), and regulatory inspectors shall have direct access to the original source records in its original recorded format: electronic or hardcopy.

TRACON (or its designee) will perform all data management functions associated with the study. Data will be captured electronically. Automated data verification ("edit checks") will be used to ensure that the data are logical and consistent. Any inconsistencies will be queried for clarification or correction as appropriate by the clinical site.

18.2. Retention of Records

To allow for appropriate evaluations and/or audits by regulatory authorities or TRACON, the Investigator agrees to keep records, including the identity of all participating patients (sufficient information to link records, CRFs and hospital records), all original signed informed consent forms, copies of all CRFs, source documents, and detailed records of treatment disposition.

Essential documents will be retained until at least 2 years after the last approval of a marketing application in an ICH region and until there are no pending or contemplated marketing applications in an ICH region or at least 2 years have elapsed since the formal discontinuation of clinical development of the investigational product. These documents should be retained for a

longer period, however, if required by the applicable regulatory requirements or by an agreement with the sponsor.

If the Investigator relocates, retires, or for any reason withdraws from the study, then TRACON should be prospectively notified. The study records must be transferred to an acceptable designee, such as another Investigator, another institution, or to TRACON. The Investigator must inform TRACON of any such transfer of responsibilities and properly identify the person or institution assuming the responsibility. The responsible investigator/institution must obtain TRACON's written permission before disposing of any records.

19. DEFINITION OF END TRIAL

19.1. End of Trial in all Participating Countries

End of trial in all participating countries is defined as the time at which the patient enrolled in the study has completed treatment on study.

For clinical investigational centers located in the EU, a declaration of the end of the clinical study will be made according to the procedures outlined in Directive 2001/20/ED, Article 10(c); for other countries, local regulations will be followed.

19.2. Study and Site Termination

Premature termination of this trial may occur because of a regulatory authority decision, change in opinion of the IRB/IEC, drug safety problems, or at the discretion of TRACON. In addition, TRACON retains the right to discontinue development of TRC253 at any time.

TRACON reserves the right to discontinue the trial prior to inclusion of the intended number of patients, but intends only to exercise this right for valid scientific or administrative reasons. If a trial is prematurely terminated or discontinued, TRACON will promptly notify the Investigator. After notification, the Investigator must contact the participating patient within a 28 day time period. As directed by TRACON, all trial materials must be collected and all CRF data must be completed to the greatest extent possible.

A study site is considered closed when all required documents and study supplies have been collected and a study-site closure visit has been performed.

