6.1.4. Treatment Period

Laboratory tests do not need to be repeated at cycle 1 day 1 if they were completed within 7 days prior in screening.

Part 1 Cycle 1

Patients will receive a single dose of TRC253 on Cycle 1 Day 1 for PK studies. No food should be consumed for at least 8 hours before and 4 hours after the TRC253 dosing. Blood pressure and heart rate will be measured prior to dose administration and hourly (± 15 minutes) for the first 6 hours following the first dose of study drug administration on Cycle 1 Day 1.

To aid in selection of the RP2D, patients may undergo PET scans using FDHT, a radiopharmaceutical specifically designed to image binding to AR. In these patients, FDHT-PET scans will be obtained before initiation of therapy. Imaging will occur at 1 or more centers under their existing IND and institutional protocol.

Safety, PD, biomarker, and disease evaluations will be performed as specified in the Time and Events Schedule for Part 1 ([Table 7](#)).

Treatment Cycles

TRC253 capsules will be self-administered once daily in the morning from Cycle 1 Day 1 onwards (Cycle 2 Day 1 onwards for Part 1). On extended PK days, no food should be consumed for at least 8 hours before and 4 hours after the TRC253 dosing. On all other days, no food should be consumed for at least 2 hours before and 1 hour after dosing.

Safety, PK, PD, biomarker, and disease evaluations will be performed at the time points specified in the Schedules of Assessments ([Table 7](#) and [Table 8](#)).

Treatment will continue until one or more of the withdrawal criterion are met (refer to [Section 7.4.3](#)).

Part 1: Once the first expansion cohort reaches its primary endpoint, patients from the dose escalation phase of the study who continue to derive benefit from TRC253 treatment will be allowed to stay on treatment and will attend monthly visits, which are to occur a minimum of once every 4 weeks (± 2 days).

Part 2: Once the primary endpoint is reached in the expansion cohort, patients who continue to derive benefit from TRC253 treatment will be allowed to stay on treatment and will attend monthly visits, which are to occur a minimum of once every 4 weeks (± 2 days).

Study procedures to be performed at the monthly visits are specified in the Schedules of Assessments ([Table 8](#)).

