6.1.5. End of Treatment and Follow-Up Period

The End of Treatment visit will be 7 days (± 2 days) after the last dose of TRC253.

The Follow-Up visit will be 28 days (± 7 days) after the End of Treatment visit. Study procedures to be performed at the follow-up visit are specified in the Schedules of Assessments ([Table 7](#) and [Table 8](#)). Patients who have unresolved study-related toxicities will have extended

follow-up once monthly until study treatment-related toxicities have resolved (baseline or \leq Grade 1) or are deemed irreversible.

Table 7: Part 1 Dose Escalation Schedule of Assessments

Study Procedures	Notes	Screening	Cycle 1 (7 days)		Cycle 2 (28 days)				Cycles 3+ (28 days)	End of Treatment	Follow-Up (EOT+28 days)
		Day -28	Day 1	Day 4	Day 1	Day 8	Day 15	Day 22	Day 1		
Screening/Administrative											
Sign main informed consent form	Informed consent must be obtained before any study-related procedures.	X									
Inclusion and exclusion criteria		X									
Brain MRI	To determine eligibility. If MRI is clinically contraindicated, a brain CT will be performed.	X									
Medical history and demographics		X									
Prior therapies		X									
Study Drug Administration											
Study Drug Administration	On extended PK days, no food should be consumed for at least 8 hr before and 4 hr after TRC253 dosing. On all other days, no food should be consumed for at least 2 hrs before and 1 hr after dosing. Patients will dose in the clinic on all PK days. Patients will track meal times on their home dosing logs.		X		Continuous daily administration from Cycle 2 Day 1 until one or more withdrawal criterion is met (see Section 7.4.3).						
Safety Assessments											
Physical examination	Full physical at screening, and targeted physical based on adverse events at subsequent visits. ECOG at screening.	X	X	X	X	X	X	X	X	X	X
Vital signs	BP, heart rate, respiration, and body temperature. In addition, on cycle 1 day 1, blood pressure and heart rate will be measured prior to dose administration and hourly (±15 minutes) for the	X	X	X	X	X	X	X	X	X	X

Study Procedures	Notes	Screening	Cycle 1 (7 days)		Cycle 2 (28 days)				Cycles 3+ (28 days)	End of Treatment	Follow-Up (EOT+28 days)
		Day -28	Day 1	Day 4	Day 1	Day 8	Day 15	Day 22	Day 1		
	first 6 hours following the first dose.										
Physical measurements	Height and weight at screening. Weight only is taken prior to each cycle and at EOT visit.	X			X				X	X	X

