Study Drug Administration	For all dosing days, no food should be consumed for at least 2 hrs before and 1 hr after dosing. Patients will dose in the clinic on all PK days. Patients will track meal times on their home dosing logs.			Continuous daily administration from Cycle 1 Day 1 until one or more withdrawal criterion is met (see Section 7.4.3).						
Safety Assessments										
Physical examination	Full physical at screening, and targeted physical based on adverse events at subsequent visits. ECOG at screening.		X	X	X	X	X	X	X	X
Vital signs	BP, heart rate, respiration, and body temperature. In addition, on cycle 1 day 1, blood pressure and heart rate will be measured prior to dose administration and		X	X	X	X	X	X	X	X

Study Procedures	Notes	Pre-Screening	Screening	Cycle 1 (28 days)				Cycles 2+ (28 days)	End of Treatment	Follow-Up (EOT+28 days)
			Day -28	Day 1	Day 8	Day 15	Day 22	Day 1		
	hourly (± 15 minutes) for the first 6 hours following the first dose.									
Physical measurements	Height and weight at screening. Weight only is taken prior to each cycle and at EOT visit.		X	X				X	X	X
Hematology	Hemoglobin, RBC count, platelet count, WBC count with differential and absolute neutrophil count.		X	X		X		X	X	(X)
Coagulation	PT, aPTT, INR, and fibrinogen.		X	X				X	X	(X)
Serum chemistry	Serum chemistry parameters are listed in Section 12.1.2 . In addition, direct bilirubin is evaluated at screening if total bilirubin is > 1.5 ULN. Iron studies (serum iron, ferritin, and total iron binding capacity).		X	X		X		X	X	(X)
Fasting lipid panel	Total cholesterol, HDL cholesterol, LDL cholesterol, and triglycerides.		X					X (Every 3 cycles: C3, C6, etc.)	X	
TSH			X					X (Every 3 cycles: C3, C6, etc.)	X	
Urinalysis	Urinalysis parameters are listed in Section 12.1.2 . If dipstick result is abnormal, microscopy will be used to evaluate sediment.		X	X				X	X	
12-lead ECG	12-lead ECGs will be performed in triplicate (approximately 2 minutes between recordings) pre-dose at all visits indicated. On cycle 1 day 15, ECGs in triplicate will be completed pre-dose and 6 hours post-		X	X	X	X (Pre-dose and 6 hours post-dose)	X	X	X	X

Study Procedures	Notes	Pre-Screening	Screening	Cycle 1 (28 days)				Cycles 2+ (28 days)	End of Treatment	Follow-Up (EOT+28 days)
			Day -28	Day 1	Day 8	Day 15	Day 22	Day 1		
	dose (+/- 15 min). Refer to Section 8.5.3 for management of QTcF prolongation.									
Pharmacokinetics and Pharmacodynamics										

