7.4.3. Patient Withdrawal Criteria

A patient will be withdrawn from the study for any of the following reasons:

1. Lost to follow-up or noncompliant

2. Withdrawal of consent
3. The sponsor terminates the study
4. Disease progression according to PCWG3 criteria ([Appendix 2](#), [Appendix 3](#))
 - a. Patients may continue on study drug if in the opinion of the Investigator, patient is deriving benefit from continuation of therapy. Continuation of therapy must be approved by the Sponsor.
5. Dose delay greater than 21 days
Note: In part 1, only patients who have received >75% of TRC253 doses during the DLT evaluation period will be considered evaluable. Patients who have received \leq 75% of TRC253 doses during the DLT evaluation period due to reasons other than toxicities, such as but not restricted to disease progression, missed appointments, non-compliance, and patient withdrawal, will be considered non-evaluable for DLT and will be replaced with a new patient.
6. Patients with AST or ALT elevations >5X ULN, or who meet Hy's Law criteria, i.e., concurrent elevation of AST or ALT >3X ULN and total bilirubin >2X ULN
7. Grade 4 adverse events
8. Patients who experience QTcF prolongation > 500 ms or > 60 ms change from baseline without electrolyte abnormalities and without response to TRC253 (See [Section 8.5.3](#))

If a patient discontinues study drug and withdraws from the study, the off-study visit assessments should be obtained.

If a patient is lost to follow-up, every reasonable effort must be made by the study-site personnel to contact the patient and determine the reason for discontinuation/withdrawal. The measures taken to follow up must be documented.

Study drug assigned to the withdrawn patient may not be assigned to another patient. Patients who withdraw for reasons other than toxicity will be replaced at the discretion of the sponsor.

If the patient withdraws consent, no further evaluation should be performed and no further attempt should be made to collect additional data. Data and samples that have already been collected will still be used as outlined in this study.

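### Section 19.2 allows up to 28 days to contact patients after any premature termination, including one for drug safety problems, although patients dose themselves daily at home and cannot stop until told

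*Combined protocol and SAP*

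**What the plan says.** Section 19.2 gives the grounds for stopping early: "Premature termination of this trial may occur because of a regulatory authority decision, change in opinion of the IRB/IEC, drug safety problems", or the sponsor's discretion. The sponsor is to notify the investigator promptly, with no number of days. The next step does have a number: "After notification, the Investigator must contact the participating patient within a 28 day time period". No ground for termination has a different limit.

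Other sections settle when dosing should end. Section 6.1.4: "Treatment will continue until one or more of the withdrawal criterion are met". Table 7 (Part 1) says "Continuous daily administration from Cycle 2 Day 1 until one or more withdrawal criterion is met", and Table 8 (Part 2) says "Continuous daily administration from Cycle 1 Day 1 until one or more withdrawal criterion is met". The list in Section 7.4.3 includes, as item 3, "The sponsor terminates the study". The synopsis presents the same list as reasons for withdrawal from treatment.

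Dosing is mostly outside the clinic. Section 6.1.4: "TRC253 capsules will be self-administered once daily in the morning from Cycle 1 Day 1 onwards" (from Cycle 2 Day 1 in Part 1). Section 8.5 has sites instruct patients on storing drug at home. Tables 7 and 8 require in-clinic dosing on PK days. The last safety visit is tied to the last dose, in Section 6.1.5: "The End of Treatment visit will be 7 days (± 2 days) after the last dose of TRC253".

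**The concern.** The stopping rule and the contact limit do not support each other. On paper, dosing ends when the sponsor terminates the study. At home, it ends when the patient hears of it, and the only stated time for that is 28 days, the length of a full treatment cycle. That may suit an administrative closure. It is long when the trial has stopped because the drug is thought unsafe.

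The stake is patient safety. The ongoing results under Section 2.4 report QTcF prolongation in 22 of 34 patients, grade 3 in two of them, and the single DLT was grade 3 QTcF prolongation at 320 mg. Section 8.5.3 has the drug held at once for a change above 60 ms or a QTcF above 500 ms. The plan also sets short limits elsewhere: 24 hours for reporting a partner's pregnancy (Section 12.3.8), and 5 business days for notifying the IRB, health authorities and sponsor after an immediate-hazard change (Section 17.1).

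**Working it through.** The 28 days is a stated rule with no formula behind it, so there is no figure of the plan's to reproduce. The check is how many doses a patient could take at home before anyone has to speak to him.

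**Inputs**
- Contact limit: 28 days from notification (Section 19.2).
- Dosing: one dose per day (Section 6.1.4), 280 mg in Part 2 (Section 8.5.2).
- Visits: Day 1 only of each 28-day cycle from Part 2 Cycle 2 on. Days 1, 8, 15 and 22 in Part 2 Cycle 1 and Part 1 Cycle 2. Window ± 2 days (Tables 7 and 8).
- In-clinic dosing on PK days. Every visit in Part 2 Cycle 1, every later Part 2 Day 1 visit, and every visit in Part 1 Cycle 2 has a PK sample.
- Home supply S, in doses: not stated. Assumed values are 7, 14 or 28.

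**Assumptions.** Day 0 is the day the investigator is notified, taken as the day of termination and falling just after a visit at which that day's dose was taken. Contact is left to the next visit or to day 28, whichever comes first. If contact is on day 28 itself, that morning's dose has already been taken.

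**Formula.** With g days to the next visit, home doses = min(S, g − 1, 28). The 1 is subtracted because the dose on the visit day is taken in the clinic.

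| Situation | g | Home doses |
|---|---|---|
| Part 2, Cycle 2 on, nominal visit | 28 | min(S, 27) = 7, 14 or 27 |
| Same, next visit 2 days late | 30 | min(S, 29, 28) = 28 with S = 28 |
| Weekly-visit cycle, nominal | 7 | 6 |
| Weekly-visit cycle, both windows used | 7 + 2 + 2 = 11 | 10, if S is at least 10 |
| Example limit of 2 business days | – | at most 4 |

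The last row takes 2 business days as at most 4 calendar days (Friday to Tuesday, no public holiday). In Part 2, 27 doses is 27 × 280 = 7,560 mg, and 4 doses is 4 × 280 = 1,120 mg.

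**End of Treatment visit.** It falls 7 ± 2 days after the last dose, that is, 5 to 9 days after it:
- last dose on day 0: days 5 to 9;
- last dose on day 4: days 9 to 13;
- last dose on day 27: days 32 to 36;
- last dose on day 28: days 33 to 37.

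Section 6.1.5 is satisfied in each case, because the visit moves with the last dose.

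**Text that might set a shorter time**
- Section 7.4.2 requires discontinuation when the investigator judges it necessary for safety. It gives no time for reaching the patient.
- Section 12.4 promises prompt written notice of new toxicity information to sites, not to patients.
- Section 17.1 allows a change before approval to remove an immediate hazard. It gives no time for telling patients.
- Sections 2.6 and 17.2 commit to GCP in general terms.

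None of these sets a limit for telling the patient.

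**The case against.** The strongest reply is that 28 days is an outer limit in a closure section, and no responsible site would wait that long after a safety stop. The sponsor must notify investigators promptly, two safety committees monitor the drug, Section 7.4.2 requires discontinuation on safety grounds, and Section 19.2 itself provides for collecting trial materials as the sponsor directs. This stands as a reason to think long delays improbable. It does not supply a limit.

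A second reply is that monitoring does not rest on the End of Treatment visit alone. In Part 2 a pre-dose triplicate ECG is due at each Day 1 visit, so in the outer-bound case the patient has just had one and the next is due at 28 ± 2 days. That also stands, and it reduces the weight of any delay to the End of Treatment visit.

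A third is that the rule may be elsewhere. The pharmacy manual, safety plan and committee charters are separate documents, and parts of the public text are withheld. This is possible and cannot be checked here.

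Two stronger readings are tempting and should be resisted. A reader might infer that Section 19.2 permits 28 more days of dosing. It does not: termination ends treatment under Sections 6.1.4 and 7.4.3. A reader might also infer a conflict with Section 6.1.5, because a last dose on the day of termination puts the End of Treatment visit well before the contact limit expires. There is none. A patient who stops on day 0 because of the termination has already been contacted, and one told later has his visit counted from his later last dose.

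**Conclusion.** The point holds as a minor patient-safety gap that is cheap to close. One contact limit of 28 days covers every premature termination, safety stops included, and no public text shortens it.

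The outer bound in Part 2 is about 27 further home doses before the next nominal visit, 28 if that visit is late within its window, and 6 (10 with both windows) in a weekly-visit cycle. It needs a safety termination, notice just after a visit, enough supply at home, and contact left as late as allowed. The dispensed quantity is an assumption, and a smaller supply lowers the bound one for one. No average, likelihood or event rate is claimed. Sample size, endpoints and analyses are untouched.

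**What to change.** In Section 19.2, keep the 28-day allowance only for terminations with no safety ground. For a termination due to drug safety problems, require the investigator to contact patients immediately on notification and within a short stated limit (for example 2 business days, a figure for the sponsor to confirm), tell them to stop TRC253 and return home supply, and schedule the End of Treatment visit as in Section 6.1.5.

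This is about two sentences in the next amendment. The downside is prompt calls by sites if a safety stop occurs. It adds no visits or data collection. If the safety plan or another study document already sets such a limit, a cross-reference in Section 19.2 would be enough.
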